Mammogram Mail- and Phone-based Interventions
(NCT 05853848)

Study Protocol with Statistical Analysis Plan

May 12, 2023

Study Protocol

Background

Mammogram screening for women, starting at age 50, can significantly reduce the risk of complications due to breast cancer. The Geisinger Health Plan (GHP) has conducted prior outreach intended to promote and increase annual mammogram screening by mailing different versions of postcards to women on the month of their 50th or 64th birthdays. The study team is working with GHP to test whether postcards or other modalities can improve upon a lack of outreach and whether live calls can improve upon other modalities, in part by making the outreach more salient and difficult to ignore, and in part by making it easier for women to schedule.

Objectives

The study will involve randomized assignment to different versions of outreach, including a current standard postcard encouraging patients to schedule their mammograms, a formal letter, an auto-dialer voice message with option to respond, and a live call from a GHP care gaps coordinator. The primary aims of this study are to evaluate, prospectively, whether live calls improve upon other outreach modalities, in terms of mammogram completion, as well as assess whether any of the outreach modalities improve upon an absence of outreach. The analyses will thus also compare each modality against (delayed) control groups consisting of contemporaneous patients randomized to intervention arms who have not yet received any outreach.

Design

This study is a randomized controlled trial with 4 study arms. The total number of initially identified eligible patients who can be contacted via both mail and phone will be divided by 7 to estimate the number of unique patients contacted across 7 sequential waves of outreach occurring from May through November 2023. At each wave, a random subset of 1/7th of the total will be randomized to arms, with slightly larger or smaller subsets selected over time if needed, to compensate for patients becoming newly eligible or ineligible over time (e.g., due to records of completed mammograms prior to the outreach date). Furthermore, a maximum of 300 live calls can be fielded per month, so randomization to the live call arm will be restricted to 300 whenever there are more than 1,200 patients to randomize in a given wave. Auto-dialer messages and live calls will be rolled out across each month, whereas postcards and letters will both be sent in two rounds per month, two weeks apart.

Methods

Female GHP members ages 51 through 74 who are overdue for an annual mammogram will be included in the study. Inclusion and exclusion criteria are largely determined by Healthcare Effectiveness Data and Information Set (HEDIS) guidelines developed by the National Committee for Quality Assurance (NCQA) to assess breast

cancer screening. Included in the intervention are women between the ages of 52 and 74, as of December 31, 2023. Excluded are women who have had a mammogram (screening, diagnostic, film, digital, or digital breast tomosynthesis) claim between October 1, 2021 and the monthly data pull preceding each monthly wave of outreach, as well as women who have not been continuously enrolled with GHP during that timeframe—i.e., they have had a gap in enrollment of greater than 45 days (or 1 month, for Medicaid beneficiaries) in a given calendar year, or any gap in enrollment between October 1 and the data pull for outreach. Also excluded are GHP members in hospice, using hospice services, or receiving palliative care in 2023. Excluded are Medicare members 66 years of age or above as of the date of the data pull for outreach who are either: (1) enrolled in an Institutional SNP any time during 2023, (2) living long-term in an institution during 2023, or (3) 66 years of age or above as of December 31, 2023 with both frailty and advanced illness (as defined by 1+ claim/encounter for frailty in 2023 and any of the following during 2022 or 2023: 2+ visits with a diagnosis of advanced illness, 1+ acute inpatient encounter with a diagnosis of advanced illness, 1+ acute inpatient discharge with advanced illness diagnosis, or a dispensed dementia medication). Finally, excluded are patients who had a bilateral mastectomy at any time before the data pull for outreach: bilateral mastectomy, unilateral mastectomy with a bilateral modifier, history of bilateral mastectomy, or any combination of codes indicating mastectomy on both left and right side. Mammogram screening evidence comes from GHP claims data, as well as Geisinger electronic health record data and St. Luke's University Health Network, WellSpan Health, PrimeMed Medical Group, Family Practice Center, and Equipt Health data, with GHP claims data trumping other sources except where claims are not on file. The intervention began on May 10, 2023.

At each wave, a random subset (as described above) of currently eligible patients will be randomized to all four of the following study arms:

1. Current **standard postcard** encouraging patients to schedule their mammograms and to contact Geisinger for help doing so.
2. **Formal letter** telling patients that they are overdue and including contact information as above
3. **Auto-dialer** voice message allowing patients to respond to schedule
4. **Live call** from a GHP care gaps coordinator helping patients schedule while speaking with them.

The remaining patients will serve as contemporaneous controls for patients in the other arms, during the span of time prior to which they are included in an active outreach arm. The controls will include patients eligible for outreach at the time the comparison patients are randomized to the corresponding active arms; they will exclude patients who become eligible at a later date. For example, controls for patients in wave 2 will consist primarily of patients assigned to wave 6, excluding those wave 6 patients who will not have been eligible for outreach at the time of the wave 2 rollout. Additionally, to account for patients who are eligible initially but become ineligible over time, those patients will be randomized to control groups as available. In the example above, a random subset of patients who become ineligible prior to the rollout of other waves will be added to the wave 2 control group.

Finally, for analysis, given that control patients do not have an intervention send date, the starting date will be randomly chosen for each to match one of the treatment arms' send dates.

Power Analysis

With 17,640 patients, we would have 80% power to detect a 2.5% absolute increase in mammograms with two-tailed alpha of .05, between each among standard postcard, letter, and auto-dialer arms, and live calls, assuming a 13.1% baseline incidence of mammograms completed within 180 days. The detectable increase becomes 1.8% when comparing across no-outreach controls and each among standard postcard, letter, and auto-dialer arms, or 3.0% across controls and live calls, assuming an 8.9% mammogram incidence within 120 days. The outcome duration varies according to the availability of appropriate comparator samples. The target effect size and number of patients are informed by practical considerations regarding the anticipated number of eligible women in 2023, the acceptable duration of the intervention (approximately 7 months), the acceptable delay between intervention and outcome being recorded, and effects that seem achievable and useful if achieved.

Project Status

Outreach has begun, as of May 10, 2023 (IVR and live calls) and May 12, 2023 (postcards and letters). No outcome data have been accessed as of the time this file was posted.

Statistical Analysis Plan

Planned Analyses

Primary Outcome: Mammogram completed

The outcome is determined according to HEDIS criteria and based on a combination of GHP claims data and other sources. The time frames vary according to the availability of appropriate comparator samples. Time frames are specified for each of the analyses below.

Question 1: Does calling people increase mammogram completions relative to other modalities of outreach?

We will test the hypothesis that live calls increase the probability of mammogram completions within 180 days of outreach, relative to other modalities.

Analysis 1 (Confirmatory): Time Frame: In the 180 days following the outreach

We will run an OLS regression including a categorical predictor variable coding for experimental arm (0 = live call, 1 = standard postcard, 2 = formal letter, 3 = auto-dialer). This analysis will include all enrolled patients.

Question 2: Do different modalities of outreach increase mammogram completions relative to no outreach?

We will test the hypothesis that each of the individual modalities increases the probability of mammogram completions within 120 days of outreach, relative to passive control groups.

Analysis 2.1 (Confirmatory): Time Frame: In the 120 days following the outreach

We will run an OLS regression including a categorical predictor variable coding for experimental arm (0 = passive control, 1 = standard postcard, 2 = formal letter, 3 = auto-dialer, 4 = live call). This analysis will include patients in the first 3 waves of active outreach, along with a passive control group consisting of the contemporaneous 120 days of the last 3 waves of outreach, during which outreach will not yet have occurred for those patients.

Other Pre-specified Outcomes

We will run the analyses described above on the following additional outcomes:

1. Mammogram completed – namely, do different modalities of outreach increase mammogram completions relative to each other? We will test whether individual modalities are differentially effective in increasing the probability of mammogram completions within 180 days of outreach, relative to each other (for those modalities not already compared by the analyses above).
[Time Frame: In the 180 days following the outreach]

We will run an OLS regression including a categorical predictor variable coding for experimental arm (0 = standard postcard, 1 = formal letter, 2 = auto-dialer), as well as a separate OLS regression (0 = formal letter, 1 = auto-dialer). This analysis will include patients in all 7 waves of outreach.

2. Breast malignancy risk detected

High risk of malignancy, among patients visiting Geisinger clinics and, as available, outside Geisinger (yes/no)

[Time Frame: In the 210 days following the outreach]

3. Mammogram appointment scheduled

Appointment scheduled for mammogram, among patients visiting Geisinger clinics (yes/no)

[Time Frame: In the 30 days following the outreach]

Covariates

An interim call to action—calling or speaking with GHP for help with scheduling—may not be as helpful for patients typically seeking care at non-Geisinger clinics as those going to Geisinger health system clinics. Also, we may not get data on mammogram completions as reliably from outside the Geisinger system. Therefore, all the regressions described above will also explore including as a covariate and interaction term whether or not the patient has an attributed Geisinger PCP.

Analysis Notes

Recent work suggests that OLS regressions are appropriate in randomized experiments with binary outcome variables such as ours (Gomila, 2021).

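### Does asking whether any modality beats no outreach require a multiplicity adjustment over the four control contrasts?

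*Combined protocol and SAP*

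**What the plan says.** The Objectives section of the protocol gives two primary aims. One is to compare live calls with the other modalities. The other is to "assess whether any of the outreach modalities improve upon an absence of outreach". The next sentence describes how the second is pursued: "The analyses will thus also compare each modality against (delayed) control groups".

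The Power Analysis section names the only significance level in the documents, a "two-tailed alpha of .05". It applies that level to pairwise comparisons, with separate detectable differences for control against each of postcard, letter and auto-dialer (1.8 points) and for control against live call (3.0 points).

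In the SAP, Question 2 reads: "We will test the hypothesis that each of the individual modalities increases the probability of mammogram completions within 120 days of outreach". Analysis 2.1, labelled confirmatory, is one OLS regression with passive control as the reference level and four arm codes. It uses the first three waves of active outreach, "along with a passive control group consisting of the contemporaneous 120 days of the last 3 waves of outreach".

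Neither part of the document mentions a multiplicity adjustment, a testing order, an omnibus test, or a rule for declaring that outreach as a whole works.

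**The concern.** Taken literally, *any* describes a union: the aim is met as soon as one of four modalities beats control. A union claim resting on four tests, each at .05, has a familywise error rate well above .05. The analysis is labelled confirmatory, so a reader may expect that rate to be controlled, or at least stated.

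The two wordings also carry different error rates. If the report concluded that outreach works because one contrast of four was significant, the conclusion would be about 3.6 times as error-prone as a single test. Choosing between the readings after seeing results would be data-driven. Settling it beforehand looked cheap, because the Project Status section says "No outcome data have been accessed as of the time this file was posted".

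**Working it through.** **Inputs.** 17,640 patients (Power Analysis) over 7 waves (Design) gives 17,640 / 7 = 2,520 per wave. At that size the cap applies: "randomization to the live call arm will be restricted to 300 whenever there are more than 1,200 patients to randomize in a given wave". Assuming that the other three arms share the remainder equally, each receives (2,520 − 300) / 3 = 740 per wave.

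- Three active waves: 3 × 740 = 2,220 in each of postcard, letter and auto-dialer; 3 × 300 = 900 live calls.
- Three control waves: 3 × 2,520 = 7,560, before changes in eligibility.
- All seven waves (Question 1): 7 × 740 = 5,180 per other arm; 7 × 300 = 2,100 live calls.

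**The plan's own power figures.** The formula is power = Φ[(d − 1.96·s0)/s1], where s0 is the pooled-null and s1 the unpooled standard error.

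| Contrast | d | s0 | s1 | Power |
|---|---|---|---|---|
| Live call v another arm, 13.1% base | 0.025 | 0.00893 | 0.00920 | 79.3% |
| Control v live call, 8.9% base | 0.030 | 0.01020 | 0.01128 | 81.3% |
| Control v each other arm, 8.9% base | 0.018 | 0.00701 | 0.00733 | 71.9% |

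The first two agree with the stated 80%. The third does not: the detectable difference comes out near 2.0 points, not 1.8. That is a separate matter. The familywise error depends on alpha, the number of contrasts and the sample-size ratios, not on the effect size.

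**Familywise error with no true effects.** If the four tests were independent:

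- two-sided: 1 − 0.95⁴ = 18.5%
- false benefit only: 1 − 0.975⁴ = 9.6%

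The shared control makes the contrasts positively correlated, with r_ij = λ_i·λ_j and λ = √(n/(n + n0)). For n = 2,220, λ = √(2,220/9,780) = 0.476; for n = 900, λ = √(900/8,460) = 0.326. The correlations are therefore 0.476² = 0.23 and 0.476 × 0.326 = 0.16. Numerical integration at a critical value of 1.96 gives:

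| Control size | Any significant, two-sided | Any false benefit |
|---|---|---|
| 2,520 | 16.4% | 8.2% |
| 7,560 (as planned) | 18.0% | 9.1% |
| 10,080 | 18.2% | 9.3% |

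The aim concerns improvement, so the relevant comparison is 9.1% with 2.5%, a ratio of 9.1 / 2.5 = 3.6. The two-sided figure also counts contrasts favouring no outreach, which could not support the claim.

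**Cost of adjusting.** With Bonferroni over four contrasts (critical value 2.498), power at the stated effects falls from 71.9% to 52.6% for 1.8 points and from 81.3% to 65.6% for 3.0 points. Detectable differences rise from 2.00 to 2.39 points and from 2.95 to 3.52 points. Dunnett's critical value, 2.484, recovers almost nothing. Holm eases the threshold only after a first rejection.

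**What the planned regression already offers.** The joint 4-df test of arm holds its own level at 5% and leaves the individual contrasts untouched. With arm rates of 8.9%, 10.7% (three arms) and 11.9%, the weighted mean is 9.87%. The between-arm sum of squares is Σn(p − p̄)² = 1.541, and the average binomial variance is 0.0889. The noncentrality is 1.541 / 0.0889 = 17.3, which gives about 93% power (chi-square approximation).

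**Which reading the text supports.** The union reading rests on one word in a narrative paragraph. The following sentence of the Objectives, the pairwise power statements and the Question 2 hypothesis are all per modality. In ordinary English, asking whether any modalities improve completion can equally mean which ones do, if any.

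**The case for a change.** The best case for a change is that a confirmatory plan should fix its claim in advance. Two wordings with different error rates coexist, nothing says which governs, and one sentence would settle it. Rewording the aim would cost no power, and the familywise figures are sound and barely move with the control size.

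The arithmetic stands, and so does the observation that the documents are silent. What does not stand is the step from silence to inflated error. The inflation arises only under a one-win rule, and no section states one. Without it, aligning the wording of the aim would alter no estimate, test or interval. Adding an adjustment would alter results, but for four different interventions that share a control and answer separate practical questions, leaving the contrasts unadjusted is a common and defensible choice, and the loss of power is large. The Power Analysis ties the sample size to practical limits, so that loss could not readily be recovered.

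The worry extends even less well to Question 1, which reads: "We will test the hypothesis that live calls increase the probability of mammogram completions within 180 days of outreach, relative to other modalities". That section has no *any* wording and no one-win rule. The corresponding rates of 10.8% two-sided and 5.4% favourable would apply only if such a rule were brought in from outside.

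**Conclusion.** No change is needed. Followed as written, Analysis 2.1 yields four per-modality answers, each with its own two-sided 5% error rate. That per-contrast level is inferred from the power paragraph, since the SAP does not restate it. The *any* phrasing is loose wording that the rest of the plan resolves.

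The size of the issue, if the results were misread, is a 9.1% chance of a false benefit claim with no true effects against 2.5% for one test, or 18.0% against 5% in both directions. This assumes 2,520 patients per wave, 300 of them live calls, equal sharing among the other three arms, and about 7,560 controls.

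A reader of the eventual report should therefore not take one positive contrast as confirmation that outreach in general works. An analyst who wants that overall statement can use the joint test of arm from the planned regression. It is non-directional and does not confirm any named modality.

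### Analysis 2.1: the rule for returning women who became ineligible to the no-outreach controls has no selection probabilities, and the SAP's control definition does not mention it

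*Combined protocol and SAP*

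**What the plan says.** Eligibility is checked again before every wave. The protocol's Methods section excludes women with a mammogram "claim between October 1, 2021 and the monthly data pull preceding each monthly wave of outreach", and at each wave "a random subset (as described above) of currently eligible patients will be randomized to all four of the following study arms". The Design section gives a recorded mammogram as an example of why women drop out of the pool: "ineligible over time (e.g., due to records of completed mammograms prior to the outreach date".

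Methods then builds the no-outreach controls from later waves. In its example, "controls for patients in wave 2 will consist primarily of patients assigned to wave 6", limited to women who were already eligible at wave 2. It adds a correction: "to account for patients who are eligible initially but become ineligible over time, those patients will be randomized to control groups as available". For wave 2 this means that "a random subset of patients who become ineligible prior to the rollout of other waves will be added to the wave 2 control group". Each control receives a start date drawn at random from the send dates of the treated arms.

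SAP Analysis 2.1 is confirmatory. It sets the first three waves against controls from the final three waves, followed over the same 120 days before their own outreach. It neither mentions the add-back nor refers to Methods for it.

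**The concern.** A woman can be drawn into wave 5, 6 or 7 only if no mammogram is on record at that wave's data pull. When she serves as a control for wave 1, 2 or 3, that pull falls near the end of her 120-day outcome window, so she has been selected partly on not having the outcome. Women in the active arms were not selected in this way.

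Returning the women who left corrects this only if they come back in the right proportion. Too few makes outreach look beneficial; too many makes it look harmful. Methods does not fix the proportion, and the SAP's definition taken literally sets it to zero. Analysis 2.1 is the only confirmatory test of outreach against no outreach. Analysis 1 does not use these controls and is unaffected.

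**Working it through.** **Inputs from the documents.** 17,640 women; seven waves, May to November (214 days); at most 300 live calls per wave; 8.9% with a mammogram in 120 days without outreach; calls starting two days before mail (Project Status) and spread over the month; "postcards and letters will both be sent in two rounds per month, two weeks apart".

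**Assumed, because not stated.** Recording lag of 0-90 days; data pull 7 or 15 days before the wave (lead); constant hazard; equally spaced waves.

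**1. The plan's yardstick.** Each wave has 17,640/7 = 2,520 women: 300 live calls and (2,520 - 300)/3 = 740 in each other arm. Three waves give 2,220 per non-call arm, 900 live calls and 7,560 controls. A two-sided 0.05 pooled test then has 81.3% power for 3.0 points (control against live call), as stated. For 1.8 points (control against another arm) it has 71.9%; 80% needs 2.0 points. That gap is a separate matter. Here 1.8 serves only as a benchmark, and 2.0 would lead to the same conclusion.

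**2. Controls from the last three waves only.** Daily hazard = -ln(1 - 0.089)/120 = 0.000777. Paired waves are 4 × 214/7 = 122.3 days apart. A control's mammogram escapes the later eligibility check only if it falls after day c = 122.3 - lead - lag. The mean start day is (1,480 × 9 + 1,040 × 15)/2,520 = 11.5, taking mail on days 2 and 16 and calls spread over 30 days. So 120 + 11.5 - c days of the window can yield an event, and the control rate is 1 - exp(-0.000777 × days):

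| Lag, lead (days) | c | Days left | Window before c | Control rate |
|---|---|---|---|---|
| 0, 7 | 115.3 | 16.2 | 87% | 1.25% |
| 30, 7 | 85.3 | 46.2 | 62% | 3.52% |
| 60, 15 | 47.3 | 84.2 | 30% | 6.33% |
| 90, 15 | 17.3 | 113.1* | 6% | 8.40% |

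*Averaged over start days, since some fall after c.

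The active rate is slightly under 8.9% because mammograms between pull and send date count as non-events. At lag 0 and lead 7 it is 8.9% × exp(-0.000777 × 18.5) = 8.8%.

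**3. The add-back proportion.** If each wave is an equal share of those still eligible, a woman who leaves between waves m and m+1 would have entered any given later wave with chance 1/(7 - m). Two plain readings of Methods give other chances. Reading A randomizes her among the control groups for whose matching wave she was eligible. Reading B randomizes her equally over all three groups and keeps her only if she was eligible at that wave.

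| Controls for | Leaving between waves | Chance needed | Reading A | Reading B |
|---|---|---|---|---|
| Wave 1 | 1-2, 2-3, 3-4, 4-5 | 1/6, 1/5, 1/4, 1/3 | 1, 1/2, 1/3, 1/3 | 1/3 each |
| Wave 2 | 2-3, 3-4, 4-5, 5-6 | 1/5, 1/4, 1/3, 1/2 | 1/2, 1/3, 1/3, 1/3 | 1/3 each |
| Wave 3 | 3-4, 4-5, 5-6, 6-7 | 1/4, 1/3, 1/2, 1 | 1/3 each | 1/3 each |

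Both readings return too many early leavers and too few of the latest.

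**4. Simulation with no outreach effect** (percentage with a mammogram; ranges depend on whether the first pool already contains unrecorded mammograms):

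| Lag, lead | Active | No add-back | A | B |
|---|---|---|---|---|
| 0, 7 | 8.7-8.8 | 1.2 | 11.2 | 9.6 |
| 30, 7 | 8.6 | 3.5 | 8.7-9.1 | 8.8-8.9 |
| 60, 15 | 8.3-8.6 | 6.3 | 8.0-8.7 | 8.4-8.7 |
| 90, 15 | 8.1-8.5 | 8.4 | 8.3-9.3 | 8.7-9.3 |

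The no-add-back column agrees with step 2. At a 15-day lag, A shows 0.9-1.2 points of spurious harm and B 0.5-0.6. If half the women are recorded at once and half after 30-60 days, omission gives 4.4-6.3 points of spurious benefit, and the two readings give 0.2-1.5 points of spurious harm.

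Without the add-back, a non-call arm is falsely declared beneficial in 100% of tests at lags of 0-30 days, 88-95% at 60 and 1-5% at 90. Under A it is falsely declared harmful in 93-94% at zero lag and 4-9% at 30 days (nominal 2.5%).

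**5. A rule using actual selection probabilities.** Controls stay within 0.1 point of the active arms at every lag from 0 to 90 days. Assuming 1% per month leaving for other reasons and 2% per month newly eligible does not change this.

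**The case against.** The strongest reply is that the plan already contains the correction. Protocol and SAP are one file with one date. Methods constructs the control group and says why women who left are returned. The SAP sentence may be shorthand; it also leaves out the start-date rule, which nobody would take as dropped. A reader might infer from the figures above that the trial will report a false benefit of 2 to 7.5 points. The documents do not support that: those figures apply only if the add-back is omitted.

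A reader might also infer that the add-back itself produces 2 to 2.5 points of false harm. That needs reading A and almost immediate recording. The exclusion is worded in terms of claims, and claims take precedence over other sources, so zero lag is an extreme case. At 30-60 days both readings are within about 0.5 point. Prompt recording for some women still cannot be excluded, because "Mammogram screening evidence comes from GHP claims data, as well as Geisinger electronic health record data".

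Finally, A and B are only two readings, and nothing in Methods rules out the correct allocation. These objections limit the likely size and stand. They leave two facts in place: the allocation is not fixed, and the section defining the confirmatory comparison does not refer to it.

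**Conclusion.** The point holds as a risk of bias from an unspecified allocation and a mismatch between protocol and SAP. It is not proof that the final estimate will be biased, nor that the protocol's intended rule is wrong.

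If the add-back is omitted, the spurious benefit reaches or exceeds the stated 1.8-point detectable effect at recording lags up to about 60 days and nearly vanishes at 90. If leavers are returned by equal chance, the error is 0.8-2.5 points of spurious harm at zero lag, 0.5-1.2 at 15 days, within about 0.5 either way at 30-60 days, and 0.2-0.9 of harm at 90. At zero lag the two equal-chance readings differ by 11.2 - 9.6 = 1.6 points, so an analyst's later choice could matter nearly as much as the target effect.

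These sizes rest on the assumed lag, data-pull lead and constant hazard. That the add-back proportion must match the chance of being drawn into the later wave does not depend on them. Analysis 2.1 is not the only comparison with no outreach, since the SAP repeats its analyses on other outcomes, but it is the only confirmatory one.

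**What to change.** Make two changes before outcome data are accessed; Project Status says none had been when the file was posted.

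- **Protocol, Methods.** Give each woman who becomes ineligible before being drawn a would-have-been wave at random, using the actual selection probability of each remaining wave (number drawn divided by number eligible and not yet drawn). Include her as a control only if that wave is 5, 6 or 7 and she was eligible at the data pull for the matching wave 1, 2 or 3.
- **SAP, Analysis 2.1.** Define the controls by that rule, or refer to it.

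The actual probabilities matter. Equal chances over the remaining waves work when each wave is an equal share of those still eligible, but leave the control rate 0.2-0.3 point low if waves are fixed at 2,520.

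The cost is two sentences, keeping the eligibility list from each monthly pull, and a little allocation work. Outreach, contacts, wave selection and the OLS model all stay as they are.

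### With 8.9% as the control rate, the stated 1.8% detectable increase for postcard, letter and auto-dialer against control has about 69–72% power, not 80%; 80% needs about 2.0–2.1 points

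*Combined protocol and SAP*

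**What the plan says.** The Power Analysis opens with the total and the error rates: "With 17,640 patients, we would have 80% power to detect a 2.5% absolute increase in mammograms with two-tailed alpha of .05". That 2.5% is for live calls against each other modality, "assuming a 13.1% baseline incidence of mammograms completed within 180 days". For the comparisons with no outreach it says: "The detectable increase becomes 1.8% when comparing across no-outreach controls and each among standard postcard, letter, and auto-dialer arms". It then gives 3.0% for live calls against controls. Both of these last figures carry one condition: "assuming an 8.9% mammogram incidence within 120 days". The 13.1% is called a baseline. The 8.9% is not tied to any group.

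Arm sizes and the power formula are not stated. Three rules let a reader infer the counts:
- Design, wave size: "a random subset of 1/7th of the total will be randomized to arms, with slightly larger or smaller subsets", with seven waves.
- Design, live-call cap: "randomization to the live call arm will be restricted to 300 whenever there are more than 1,200 patients to randomize in a given wave".
- SAP, Analysis 2.1, comparison sets: "the first 3 waves of active outreach, along with a passive control group consisting of the contemporaneous 120 days of the last 3 waves".

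**The concern.** The two detectable increases against control, 1.8% and 3.0%, appear in one sentence under one assumed rate. They should therefore follow from one set of counts and one formula. With the counts that the design implies, 3.0% follows and 1.8% does not.

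The 1.8% covers three of the four contrasts in Analysis 2.1, which is confirmatory and serves one of the two primary aims. If the true effect of a postcard, letter or auto-dialer message were 1.8 points, the chance of missing it would be about 28–31% per contrast, not the 20% implied. A reader who uses the stated figure to judge how informative a non-significant contrast is would give it too much credit.

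**Working it through.** **Counts**
- Wave size: 17,640 / 7 = 2,520.
- Live calls: 300 per wave, because 2,520 exceeds 1,200.
- Each other arm: (2,520 − 300) / 3 = 740 per wave. The equal split is an assumption.
- Analysis 1, seven waves: 7 × 740 = 5,180 per non-call arm and 7 × 300 = 2,100 live calls.
- Analysis 2.1, three active and three control waves: 3 × 740 = 2,220 per non-call arm, 3 × 300 = 900 live calls and 3 × 2,520 = 7,560 controls.

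**Formulas** (comparator C, arm A, difference d, two-sided 0.05)
- SE0 = √[p̄(1−p̄)(1/nC + 1/nA)], where p̄ is the pooled rate.
- SE1 = √[pC(1−pC)/nC + pA(1−pA)/nA].
- Pooled: power = Φ[(d − 1.96·SE0)/SE1].
- Unpooled: power = Φ[d/SE1 − 1.96].
- Arcsine: power = Φ[h·√(nC·nA/(nC+nA)) − 1.96], where h = 2·asin√pA − 2·asin√pC.

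**The two companion figures**
- 2.5% (13.1% vs 15.6%, 5,180 vs 2,100): SE0 = 0.00893, SE1 = 0.00920, pooled power 79.3%.
- 3.0% (8.9% vs 11.9%, 7,560 vs 900): SE0 = 0.01020, SE1 = 0.01128, pooled power 81.3%; arcsine 79.8%.

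Both agree with the plan, which supports the inferred counts and 8.9% as the control rate.

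**The 1.8%** (8.9% vs 10.7%, 7,560 vs 2,220)
- p̄ = (7,560 × 0.089 + 2,220 × 0.107) / 9,780 = 0.0931; SE0 = 0.00701; SE1 = 0.00733.
- Pooled: (0.018 − 1.96 × 0.00701) / 0.00733 = 0.58, power 71.9%.
- Arcsine: 0.0606 × 41.4 − 1.96 = 0.55, power 70.9%.
- Unpooled: 0.018 / 0.00733 − 1.96 = 0.49, power 69.0%.
- Simulation of the planned five-arm OLS (200,000 runs): 70.2%.

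**Increase detectable with 80% power (points)**

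| Contrast | Plan | Pooled | Arcsine | Unpooled |
|---|---|---|---|---|
| Live call vs other modality | 2.5 | 2.53 | 2.54 | 2.58 |
| Live call vs control | 3.0 | 2.95 | 3.01 | 3.18 |
| Non-call arm vs control | 1.8 | 2.00 | 2.02 | 2.07 |

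**Could another assumption explain 1.8%?**
- *Rounding.* At 1.85 points, power is 71–74%.
- *Number of controls.* At 1.8 points, 5,040 controls give 65–67% power and 10,080 give 71–74%. Even 15,120 give at most 77.1% (pooled).
- *Unequal split.* With 7,560 controls, each non-call arm needs 2,925 (pooled), 2,979 (arcsine) or 3,127 (unpooled) women. Three arms then need about 8,775–9,382. Waves 1–3 supply 3 × 2,220 = 6,660 outside the live-call arm and 7,560 in all.
- *Larger waves.* Even the pooled figure needs (8,775 + 900) / 3 = 3,225 women per wave. That is 28% above 2,520, more than the slight variation the Design section allows.
- *Four active waves* (2,960 and 1,200 vs 7,560). These give 1.79–1.84 for non-call arms but 2.59–2.75 for live calls, and they contradict Analysis 2.1.
- *8.9% as the outreach-arm rate.* This gives 1.81 (pooled), 1.83 (arcsine) or 1.88 (unpooled) for non-call arms, but 2.55, 2.61 or 2.77 for live calls.
- *One-sided 0.05.* Power at 1.8 points is 79–81%, but the plan states "with two-tailed alpha of .05".

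**The case against.** The strongest objection is that the text does not say which group has the 8.9% rate. The 13.1% baseline belongs to a contrast among outreach arms. Read the same way, 8.9% would be an outreach-arm rate, and about 1.8 follows from the same counts. The figure out of line would then be 3.0%, and it would err on the cautious side. The case for 8.9% as the control rate rests on one companion figure, because the 2.5% uses a different rate. This stands as a caveat on which figure is wrong. It does not remove the error, since under that reading the 3.0% fails.

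The counts are also inferred. The Methods section drops later-eligible women from the controls and adds some who become ineligible, so 7,560 is approximate. That widens the power range to about 65–74% but does not bring it to 80%. Rounding narrows the shortfall to about 6–9 points at best.

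Finally, the consequence is limited. The Power Analysis says the number of patients and the target effect reflect practical considerations, and a null result is better judged from its confidence interval than from a planning figure. Both points are fair. They bear on how much the error matters, not on whether the figure is right.

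**Conclusion.** The concern holds. With 8.9% as the control rate and about 2,220 women per arm against 7,560 controls, power at 1.8 points is 69.0–71.9%, a shortfall of about 8–11 percentage points. The increase detectable with 80% power is 2.00–2.07 points.

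This rests on equal waves, an equal split of women not assigned to live calls, and roughly three waves of controls. Varying the split or the number of controls does not rescue the figure. What does not depend on the meaning of 8.9% is that no reading tried yields both 1.8% and 3.0%, so at least one needs correcting. The 1.8% is the likelier one, because the control-rate reading reproduces the 3.0%. The effect on the trial is moderate: no sample size, allocation or analysis depends on the figure.

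**What to change.** In the Power Analysis:
1. State the counts behind each figure (about 2,220 per non-call arm, 900 live calls and 7,560 controls for Analysis 2.1, if the split is equal) and the formula used.
2. Say whether 8.9% is the no-outreach rate.
3. If it is, restate the detectable increase for postcard, letter and auto-dialer against control as about 2.0%, or keep 1.8% and state about 70% power. If 8.9% is the outreach-arm rate, correct the 3.0% for live calls instead.

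The cost is one less favourable planning figure (or, in the other case, a smaller one for live calls) and one added sentence. The Project Status section says no outcome data had been accessed at posting, and the change concerns only planning assumptions, so results do not bear on it.
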